3.2.3 Exploratory Endpoints

[REDACTED]

3.3 Treatments

For this study, the terms investigational drug and study medication refer to IMCnyeso.

Patients enrolled in this study will receive treatment with single agent IMCnyeso, dosed weekly on Days 1, 8, 15 and 22 until disease progression or other reason to discontinue. Patients will be hospitalized for 2 nights following the administration of the first dose (C1D1) of IMCnyeso and

will remain at the site for overnight observation following administration of the second dose (C1D8). In addition, patients receiving intra-patient escalation (IPE) will be hospitalized overnight following the first three doses (C1D1, C1D8, and C1D15). After reviewing safety, PK, and cytokine data from at least 3 patients enrolled at a given dose level, the SST may decide that one night of hospitalization is adequate after the first dose for subsequent patients (with longer hospitalization if indicated). After Phase I is completed and the SST would review all available relevant data for at least 6 patients at the RP2D, the SST may decide to reduce the minimum required monitoring time during the Phase II portion of the study to no less than 8 hours post-end of infusion on C1D1, C1D8, and/or C1D15 (with longer hospitalization if clinically indicated). Patients who experience certain AEs may require additional in-patient monitoring as described in Section 6.15 of Protocol V4.0.

For each patient, the first dose will be infused over 2 hours (± 15 minutes); for dose levels ≤ 30 mcg; the first dose may be infused over 1 hour (± 10 minutes). If the first dose is well tolerated without \geq Grade 2 infusion and/or a hypersensitivity reaction, a given patient's subsequent infusion times may be reduced to 1 hour (± 10 minutes) starting at C1D8, and further reduced to 30 minutes (± 10 minutes) starting at C3D1 provided the above conditions continue to be met. Investigators may prolong the infusion time for individual patients if medically indicated at any time.

Cohorts 1- 4 would be fixed dose and cohorts 5 - 7 will introduce an intra-patient escalation (IPE). If the severity of cytokine-mediated AEs tend to become less severe following the initial doses of study drug using a fixed-dose regimen, the SST may initiate a step 1 IPE regimen, in which a lower dose is given on Cycle 1 Day 1 and a higher (target) dose is given on Cycle 1 Day 8 and beyond (for details: Section 6.10.1 of the Protocol V4.0).

3.4 Dose Adjustment/Modifications

All doses administered to subsequent cohorts of patients will be determined by the SST and will be guided by the BLRM and will be subject to both the EWOC principle and the escalation rule. Dose-escalation decisions will be made by the SST, which will consist of the Study Investigators, the Sponsor Medical Monitor, and a Statistician. For each cohort, dose escalation or de-escalation decisions will be based on the SST's review of all relevant data available, from all dose levels evaluated in the ongoing study, including safety information, DLTs, all \geq Grade 2 toxicity data, PK, and pharmacodynamic data from evaluable patients (as defined in Section 6.10.2 of protocol version 4.0). The data and BLRM dose recommendations will be discussed and agreed upon during the dose-escalation teleconference (DETC), and all decisions will be documented in the meeting minutes and shared with all participating Principal Investigators.

The actual dose levels that have been tested in this study are shown in **Table 1** below. Actual doses will be determined using the BLRM and must be agreed upon by the SST.

Table 1 - IMCnyeso Dose Levels for Phase I Dose Escalation

Cohort number	Cohort description	IMCnyeso Dose(s) Tested	Enrollment (n)
1	3 mcg fixed dose	3 mcg	4
2	10 mcg fixed dose	10 mcg	3
3	30 mcg fixed dose	30 mcg	5
4	100 mcg fixed dose	100 mcg	3
5	30-100 mcg intra-patient dose escalation	30-100 mcg	5
6	30-100-180 mcg intra-patient dose escalation	30-100-180 mcg	4
7	30-100-300 mcg intra-patient dose escalation	30-100-300 mcg	6 (planned)

To better understand the safety, tolerability, and PK profile of single agent IMCnyeso, additional cohorts of patients may be enrolled at preceding dose levels or intermediate dose levels, before or in parallel, while proceeding with further dose escalation. The outcome from these cohorts will be included in the BLRM.

If the first 2 patients in a previously untested dose level experience a DLT, additional enrollment in that cohort will stop, the BLRM will be updated with this new information, and the SST will evaluate the available safety, PK, and pharmacodynamic data. By incorporating information gained at the preceding dose levels and provided the BLRM predicts that the risk of excessive toxicity remains below 25% (EWOC), additional patients may be enrolled at this dose level or a lower dose level as agreed upon by the SST.

If the severity of cytokine-mediated AEs tend to become less severe following the initial doses of study drug using a fixed-dose regimen, the SST may initiate step 1 intra-patient escalation regimen, in which a lower dose is given on Cycle 1 Day 1 and a higher (target) dose is given on Cycle 1 Day 8 and beyond. Further details can be found in Section 6.10.1 of the protocol.

A subsection on dose escalation decisions will be included in the CSR, and the BLRM outputs produced for the dose escalation meetings will be included in the CSR appendices.

4 General Statistical Considerations

Categorical data will be summarized using frequencies and percentages. The denominator for all percentages will be the number of patients belonging to the analysis set of interest by dose group or disease cohort according to the particular summary. Percentages will be presented as integer numbers with no decimal part given the small number of patients enrolled. Percentages will not be displayed for 0 frequencies. A row denoted “Missing” will be included in count tabulations where necessary to account for missing values.

For continuous data, the mean, standard deviation (SD), median, minimum (Min) and the maximum (Max) will be presented. For PK, if concentration results below a lower limit of detection (LLOD) and LLOD for a parameter is clinically relevant then it will be included in the calculation of standard statistics with that concentration result set at 0; but for cytokines it will be set at the midpoint between 0 and the LLOD. Minimum and maximum will be presented to the same number of decimal places as the raw data, mean and median will be presented to 1 more

decimal place than the raw data, and standard deviation will be presented to 2 more decimal places than the raw data.

No formal statistical hypotheses will be tested. Where appropriate, two-sided 95% confidence intervals will be presented.

All data summaries and statistical analyses will be performed using the SAS software Version 9.4 or higher (SAS Institute, Cary, NC).

The study day of an event that occurred after or on the first dose date will be calculated as:

Event Date – C1D1 Date + 1

whereas the study day of an event that occurred before the first dose date will be calculated as:

Event Date – C1D1 Date

All listings will be sorted for presentation in order of center and patient identification number. Key variables to be displayed on each listing will be: Study phase, center, patient identification number, age, sex, and race.

The following rules will be followed for reporting results unless stated otherwise:

- Screen failure patients are those who signed the ICF, but never started the study treatment for any reason. For these patients, the eCRF data collected will not be included in analyses but will be reported in the clinical study report as separate listing.
- Baseline is defined as the last assessment prior to the first dose of treatment received (e.g. C1D1 pre-dose).
- Tables, listings, and figures will be presented for Phase I and II separately or combined Phase I/II together as appropriate.
- Tables for DLTs will be produced for Phase I and Phase II.
- Visit time points will be presented in the form Cycle x Day y.

Unless otherwise stated in below sections, missing data will not be imputed, but they will simply be noted as missing on appropriate tables/listings.

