1.4 Clinical Safety and Experience

This is the first-in-human (FIH) study of IMCnyeso. As of 22Jan2020, 15 patients have been enrolled and treated (n=4 at 3 mcg; n=3 at 10 mcg; n=5 at 30 mcg, and n=3 at 100 mcg). No dose-limiting toxicity (DLT), treatment-related \geq Grade 3 adverse event (AE), AE leading to discontinuation, or fatal AE has been reported. Treatment-related serious AEs (SAEs) were reported in 2 patients; a Grade 1 overdose (attributed to dose-preparation error) was reported in Cohort 1 (3 mcg) and an event of Grade 2 CRS was reported in Cohort 4 (100 mcg). The most commonly reported AEs (including reported signs and/or symptoms of CRS) were headache (n=10, 67%) and fatigue and pyrexia (each n=9, 60%). These data are from an ongoing study, are not fully validated, and potentially subject to change prior to final database lock.

Characterization of safety, tolerability, PK, pharmacodynamics, and efficacy are ongoing.

Based on the available IMCnyeso preclinical data, the IMCnyeso mechanism of action, and clinical safety information from the tebentafusp clinical trials, IMCnyeso may elicit the following adverse drug reactions:

Cytokine Release Syndrome: Release of pro-inflammatory cytokines (eg, IL-6, IFN- γ , TNF- α) is a predicted pharmacodynamic effect of IMCnyeso. Based on experience with tebentafusp,

symptoms such as pyrexia, chills, nausea, hypotension, and edema were observed in most patients, typically 4-24 hours after the first 2-3 doses. As of August 2018, 2% of patients in the IMCgp100-102 study experienced severe (Grade 3) CRS with tebentafusp. Based on a shared mechanism of action with tebentafusp and non-clinical assessments of both molecules in whole blood assays, the risk of CRS with IMCnyeso is anticipated to be similar to tebentafusp. Fully functional resuscitation equipment and medications to handle acute infusion-related emergencies (eg, anaphylaxis, CRS) must be available at each study site. Patients will be hospitalized after the initial doses of IMCnyeso for monitoring (see [Section 6.2](#)). Scheduled samples will be taken for cytokine monitoring and additional samples should be taken in the event of suspected CRS. The protocol provides instructions on the recognition and conservative management of associated symptoms.

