9.5 Primary Analysis Variables

9.5.1 Phase I: DLT

In Phase I, the primary variable is the occurrence of 1 or more DLTs. An adaptive BLRM guided by the EWOC principle will be used to guide dose recommendations and estimate the MTD, as described in [Section 6.10](#) and [Section 13.3](#).

Patients in Phase I who are ineligible for the DDS will be excluded from the primary analysis, although their data will be used for all remaining analyses.

As a supportive analysis in the Phase I dose escalation part of the study, a dose-exposure relationship may be estimated for IMCnyeso via a BLRM to further guide the dose recommendation to targeted exposure of IMCnyeso. From the estimation of the dose-exposure model, the following posterior summaries will be derived for each dose:

- Mean, median, standard deviation, and 95%-credible interval for the exposure
- The probability that the true AUC after first dose of treatment achieves the target exposure

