4.2.1 Treatment and Disease Groups for Reporting

The Phase I safety data will be listed, summarized, and analyzed overall and by dose group where dose groups may incorporate pooling of dose levels; the exact extent of pooling will be defined after Phase I actual doses administered are known, and is expected to use the Recommended Phase 2 dose (RP2D) as threshold (see **Table 2**).

Patients who enroll in multiple cohorts will be represented once for each cohort and once in the total/overall study columns for summaries that are based on baseline data (e.g. demographics, medical history). Listing will be presented for patients who are escalated to a higher dose.

Table 2 – Potential Phase I Dose Groups

Treatment Group	Dose Group (Label for TLF Reporting)*	Patients included
IMCnyeso < x mcg QW	< RP2D	All Phase I dose escalation cohorts receiving a dose less than RP2D
IMCnyeso = x mcg QW	= RP2D	All Phase I dose escalation cohorts receiving the same dose as RP2D
IMCnyeso > x mcg QW	> RP2D	All Phase I dose escalation cohorts receiving a dose greater than RP2D

* x mcg is the Recommended Phase 2 Dose (RP2D) where x is determined during Phase I and administered IV over 1-2 hours.

In Phase II, patients will be analyzed according to the disease cohorts laid out in **Table 3**.

Table 3 - Phase II Disease Cohorts at RP2D

Cohort	Disease Cohort
Cohort 1	Advanced NSCLC
Cohort 2	Urothelial Cancer
Cohort 3	Synovial Sarcoma

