7.2.2 Treatment Compliance and Modifications

Study treatment will be administered to the patient at the study site by trained study staff. Patients compliance with the prescribed regimen will be assured as all administrations will be performed by site staff under the supervision of the study investigator or his/her designee. Therefore, no analysis of compliance is planned. However, dose interruptions and reductions may occur (see Section 8.6).

8 Safety Analysis

Safety analysis will be conducted on the SAF for the Phase I dose escalation and separately for the Phase II expansion cohorts. Combined outputs for safety may be produced based on the Safety RP2D Analysis Set.

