8.1 Dose-Limiting Toxicity

The incidence of DLTs is the primary endpoint in Phase I. The specific type and grades of AEs classified as a DLT can be found in the protocol in Section 6.12. The DLT observation period for the Phase I dose escalation cohorts is explained in Section 3.4.

The number and percentage of patients with at least one DLT will be presented by dose group (as defined in Section 4.2.1).

A listing of key information for DLTs will be presented including patient identification number, Preferred Term (PT) of corresponding AE and CTCAE grade. DLT information will be reported and summarized for Phase II whenever appropriate

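### The SAP plans no final BLRM estimate on the dose-determining set: Phase I DLTs reach the report only as crude percentages and archived meeting outputs

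*SAP*

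**What the plan says.** **Protocol.** Section 9.5.1, under the primary analysis variables, states: "An adaptive BLRM guided by the EWOC principle will be used to guide dose recommendations and estimate the MTD". It also excludes Phase I patients who do not qualify for the DDS from the primary analysis. Section 6.11 sets three conditions for the MTD. The first is at least 6 patients treated at the dose and regimen. The other two are posterior statements: the dose has the highest probability of a true DLT rate in 16%–33%, and the probability of excessive toxicity is below 25%. The RP2D must not exceed the MTD.

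**SAP.**
- 3.4: "the BLRM outputs produced for the dose escalation meetings will be included in the CSR appendices", together with a CSR subsection on the escalation decisions.
- 4.3.6: the DDS guides escalation and is not used as an analysis set in final reporting.
- 8 (opening): "Safety analysis will be conducted on the SAF for the Phase I dose escalation".
- 8.1: "The incidence of DLTs is the primary endpoint in Phase I", and "The number and percentage of patients with at least one DLT will be presented by dose group", plus a DLT listing.
- 4: "Tables for DLTs will be produced for Phase I and Phase II".
- 4.2.1, Table 2: the potential dose groups lie below, at and above the RP2D. The middle one is "All Phase I dose escalation cohorts receiving the same dose as RP2D".
- 11: the BLRM is updated after each escalation cohort, and the MTD/RP2D is determined at the end of Phase I.
- 12: no substantial change from protocol version 4.0 is declared.
- 14.2: the planned list contains neither a BLRM table nor a DLT table.

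**The concern.** Phase I asks which dose has an acceptable DLT risk, and the protocol answers with a model and a defined population. Followed as written, the SAP gives neither on cleaned data. The CSR would hold a crude percentage in a different population, next to printouts made for decisions during the trial.

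If a DLT or evaluability call changes after the last meeting, the printouts and the DLT listing will disagree, and nothing in the plan reconciles them. A reader of the CSR could not check on final data whether the declared MTD meets conditions 2 and 3 of protocol 6.11. There would also be no final posterior DLT risk, or interval, for the dose taken into Phase II.

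**Working it through.** **1. Passages side by side**

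| Item | Protocol | SAP, final reporting |
|---|---|---|
| Method | BLRM estimates the MTD (9.5.1) | n (%) by dose group (8.1); meeting outputs appended (3.4) |
| Population | DDS (9.5.1) | SAF (8); DDS not used (4.3.6) |
| Unit | dose and regimen (6.11) | potential groups labelled by dose relative to the RP2D (4.2.1) |
| MTD criterion | posterior probabilities (6.11) | none on final data |
| Declared as a change | – | no (12) |

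The documents state no figure for this analysis, so there is nothing to reproduce. Steps 2 and 3 only give a sense of scale.

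**2. Crude percentage (exact Clopper-Pearson 95% intervals)**
- 0/6: upper limit 45.9%.
- 1/6 = 16.7% (0.4% to 64.1%).
- Effect of the population, assuming 6 treated, 5 of them DLT-evaluable, and 1 DLT: SAF 1/6 = 16.7%; DDS 1/5 = 20.0% (0.5% to 71.6%).

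A percentage of this kind cannot show whether P(excessive toxicity) is below 0.25.

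**3. Sensitivity of the model to one DLT call**

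Inputs:
- Model (protocol 13.3.1): logit(p) = α + exp(γ)·dose.
- Prior (Table 13-6, where the γ row is labelled β): α ~ N(−2.95, 2.75²), γ ~ N(−5, 2.75²), ρ = 0.
- Pseudo-patients: Table 13-7.
- Cohort sizes: SAP Table 1, coded at the target dose. 4 at 3 mcg, 3 at 10, 5 at 30, 3 + 5 = 8 at 100, 4 at 180, 6 planned at 300.
- Excessive toxicity: p ≥ 0.33 (Table 13-5).
- Assumed: no DLT at any other dose, and all data at full weight.

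The posterior was computed on a grid.

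| Dose and data | Mean DLT risk | P(excessive) |
|---|---|---|
| 180 mcg, 0/4 | 0.09 | 0.02 |
| 180 mcg, 1/4 | 0.19 | 0.16 |
| 180 mcg, 2/4 | 0.34 | 0.48 |
| 300 mcg, 1/6 | 0.14 | 0.07 |
| 300 mcg, 2/6 | 0.25 | 0.28 |

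The 180 mcg rows use cohorts 1 to 6 only. Without pseudo-patients, P(excessive) at 300 mcg goes from 0.04 (1/6) to 0.23 (2/6).

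**4. Limits of step 3**
- The written prior does not reproduce Table 13-8. At 100 mcg it gives mean 0.252 and P(excessive) 0.283, against 0.297 and 0.323 in the table.
- The 300 mcg rows extend a model specified for 1 to 200 mcg. Protocol 13.3.1 provides for a separate model up to 350 mcg after intra-patient escalation (IPE), with its own prior, which is not given. It also down-weights data from other schedules.
- The lower step doses of the IPE regimens are ignored.

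**The case against.** The strongest reply is that neither document promises a refit. Protocol 9.5.1 refers to 6.10 and 13.3, which describe a decision tool used during the trial, and 6.11 governs how the dose is chosen rather than a re-test at database lock. Escalation meetings wait until the whole cohort has completed DLT evaluation (protocol synopsis). At least 6 patients must complete the DLT period at the RP2D before Phase II opens (6.11). Patients added at earlier doses enter the BLRM (SAP 3.4). The last update should therefore cover every cohort.

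Most of this stands, and it narrows the exposure to calls that change after the last meeting. The documents give no rate for such changes. The caveat in protocol 1.4 that data "are not fully validated, and potentially subject to change prior to final database lock" concerns a background safety snapshot and is weak support. Protocol 6.12 does let the Study Safety Team count events outside the evaluation window as DLTs, but that is the same team that sets the dose.

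The reply does not explain why 9.5.1 names a population for the primary analysis that SAP 4.3.6 then bars from final reporting, or why section 12 does not say so.

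A reader might infer that DLT risk at the RP2D is never estimated, or that only meeting outputs are reported. The documents do not support that: SAP 8.1 gives an observed percentage, Table 2 has an RP2D group, and section 4 promises DLT tables. Nor do they support saying that 2/6 at 300 mcg would fail the overdose limit. Without pseudo-patients the figure is 0.23, and other weightings gave 0.22 to 0.31.

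The simulation plan, report and addenda cited in SAP 14.1 were not available and might describe a final run.

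**Conclusion.** The point holds in limited form. Final reporting contains observed DLT percentages and archived model outputs, but no BLRM estimate in the protocol's primary-analysis population on cleaned data. This departs from protocol 9.5.1 and is not declared. It should be corrected, because conditions 2 and 3 of 6.11 cannot otherwise be checked on final data.

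The size depends on whether a DLT or evaluability call changes after the last meeting. If one does, with 4 to 6 patients at the dose, P(excessive toxicity) can move to about 0.25 or beyond: 0.16 to 0.48 in the 180 mcg illustration, and 0.07 to 0.28 or 0.04 to 0.23 at 300 mcg. These values rest on assumed DLT data, full weighting and a prior that does not match the protocol's own table. The conclusion about the missing analysis rests on the text and does not need them.

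**What to change.** - Amend SAP 4.3.6 and 8.1 to add one final BLRM run on the DDS from the cleaned or locked data, by regimen and with the model actually in force under protocol 13.3.1.
- For each dose tested, report the posterior mean DLT rate, the 95% credible interval and the probabilities of under-dosing, target and excessive toxicity.
- State whether the declared MTD meets conditions 2 and 3 of protocol 6.11 and whether the RP2D does not exceed it. Explain any difference from the last meeting output.
- Add this table and the DLT table promised in SAP 4 to 14.2, showing the DLT percentage on the DDS as well as the SAF.
- Record the change in section 12. If the simulation documents already specify a final run, cite it in 8.1.

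The cost is one more run of an existing program and a little extra tabulation. The downside is that the final estimate may differ from the one used to choose the dose, and the CSR would have to explain this.

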4.1 Sample Size

Dose decisions will be guided by the BLRM. Among the simulations that were conducted, the mean sample size was 27 patients, and the sample size was less than 33 patients in over 80% of simulations.

A Simon two-stage design will be used for each Phase II cohort using a 10% probability of a Type 1 error, a 20% probability of a Type 2 error, and assuming a target response rate of 20% versus 5% response rate for available treatment options. If there are no responses among the first 9 patients in a cohort, then accrual in that cohort will stop. If there is at least one response, at the discretion of the sponsor up to an additional 15 patients may be accrued for a total of up to 24 patients (with at least 3 responses to support further evaluation).

4.2 Randomization, Stratification, and Blinding

The Integrated Response System (IRS) will be used to control patient allocation to treatment and ensure the dosing intervals and cohort recruitment comply with the protocol.

4.2.1 Treatment and Disease Groups for Reporting

The Phase I safety data will be listed, summarized, and analyzed overall and by dose group where dose groups may incorporate pooling of dose levels; the exact extent of pooling will be defined after Phase I actual doses administered are known, and is expected to use the Recommended Phase 2 dose (RP2D) as threshold (see **Table 2**).

Patients who enroll in multiple cohorts will be represented once for each cohort and once in the total/overall study columns for summaries that are based on baseline data (e.g. demographics, medical history). Listing will be presented for patients who are escalated to a higher dose.

Table 2 – Potential Phase I Dose Groups

Treatment Group	Dose Group (Label for TLF Reporting)*	Patients included
IMCnyeso < x mcg QW	< RP2D	All Phase I dose escalation cohorts receiving a dose less than RP2D
IMCnyeso = x mcg QW	= RP2D	All Phase I dose escalation cohorts receiving the same dose as RP2D
IMCnyeso > x mcg QW	> RP2D	All Phase I dose escalation cohorts receiving a dose greater than RP2D

* x mcg is the Recommended Phase 2 Dose (RP2D) where x is determined during Phase I and administered IV over 1-2 hours.

In Phase II, patients will be analyzed according to the disease cohorts laid out in **Table 3**.

Table 3 - Phase II Disease Cohorts at RP2D

Cohort	Disease Cohort
Cohort 1	Advanced NSCLC
Cohort 2	Urothelial Cancer
Cohort 3	Synovial Sarcoma

